### **9.3 SELECTION OF STUDY POPULATION**

The number of males and females will be approximately equal in both age groups (7-11 years of age and 12-17 years of age) with at least 40% of the patients between 7 to 11 years of age. There should be reasonable representation overall of ethnic and racial minorities, reflecting the proportions in the disease population.

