#### **9.1.1 Screening Period**

The screening/washout period will generally be 1 week prior to Baseline (Visit 2), but may be extended up to a total of 5 weeks to accommodate prior medication washout or to repeat assessments (with prior approval of the Study Physician or designee). Patients will not receive any investigational product during the screening period. Patients meeting the eligibility criteria at the end of Baseline (Visit 2) will be randomized in a ratio of 2:2:1 to 1 of 3 treatment groups: placebo, vilazodone, or fluoxetine.

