#### **9.1.2 Double-blind Treatment Period**

Approximately 400 patients are planned for enrollment in the double-blind treatment period (160 placebo patients, 160 vilazodone patients, and 80 fluoxetine patients); randomization will be stratified by study center and by country.

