#### **9.7.5.1                   Primary Efficacy Parameter**

The change from baseline to Week 8 of the double-blind treatment period in CDRS-R total score will be the primary efficacy parameter. The primary analysis for comparing vilazodone versus placebo will be performed with treatment group, pooled study center, visit, and treatment group-by-visit interaction as the fixed effects and the baseline value and baseline value-by-visit interaction as the covariates. An unstructured covariance matrix will be used to model the covariance of within-patient scores. The Kenward-Roger approximation ([Kenward and Roger, 1997](#)) will be used to estimate denominator degrees of freedom. This analysis will be performed based on all postbaseline scores using only the observed cases without imputation of missing values.

In addition, 2 sensitivity analyses, LOCF and pattern-mixture model approaches, will be performed on the primary efficacy parameter. The LOCF approach is based on an analysis-of-covariance model including treatment group and pooled study center as factors and baseline CDRS-R total score as a covariate.

The other sensitivity analysis using a pattern-mixture model based on nonfuture dependent missing value restrictions ([Kenward et al, 2003](#)) will be performed to assess the robustness of the primary MMRM results to the possible violation of the missing-at-random assumption. The details of this sensitivity analyses are as follows:

[figure not shown]
The pattern for the pattern-mixture model will be defined by the patient's last visit with observed value. The observed CDRS-R total score at a visit is assumed to have a linear relationship with the patient's prior measurements. The missing values will be imputed under the assumption that the distribution of a missing observation differs from the observed only by a shift parameter value  $\Delta$ . The dataset with missing values will be analyzed using an analysis-of-covariance model with treatment group and pooled study center as factors and baseline CDRS-R total score as a covariate for between-treatment group comparisons at Week 8. The imputation of missing values and the analysis will be performed multiple times and the inference of this sensitivity analysis will be based on the combined estimates using the standard multiple imputation technique. The values for  $\Delta$  will be selected as 0 to 6 based on experience with historical data.

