9.2 MEASUREMENT OF TREATMENT COMPLIANCE

[REDACTED]

10.0 **EFFICACY ANALYSES**

The efficacy analyses will be based on the ITT Population. *Baseline* for efficacy is defined as the last nonmissing efficacy assessment (at or prior to Visit 2) before the first dose of double-blind investigational product. All statistical tests will be 2-sided hypothesis tests performed at the 5% level of significance for main effects. All confidence intervals will be 2-sided 95% confidence intervals, unless stated otherwise.

For efficacy analyses in which study center is a factor, a small center will be defined as a center with fewer than 2 patients in any treatment group in the ITT Population. Small centers will be pooled to form pseudo-centers so that each treatment group includes at least 2 ITT patients within the center. Pooling will be done (within each country first) using the following algorithm:

Based on the number of ITT patients, small centers will be ordered from the largest to the smallest, and centers of the same size will be ordered from the largest center code to the smallest center code. The pooling process starts with the largest small center from the top, which will be pooled with the smallest from the bottom until a non-small pseudo center is formed. The process will be repeated using the small centers left out after the first pass. If any centers are left out at the end of the process, they will be pooled with the smallest pseudo center. If there is more than 1 smallest pseudo center, the pseudo center with the smallest center code will be selected. In case that the pseudo center formed by pooling all small centers is still a small center, it will be pooled with the smallest non-small center. If there is more than 1 smallest non-small center, the one with the smallest center code will be selected.

These pseudo-centers will be used for all efficacy analyses when the model is adjusted for study center.

By-visit analyses based on the mixed-effects model for repeated measures (MMRM) using the observed case (OC) approach will be performed for all continuous efficacy parameters with multiple post-baseline measurements.

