10.1 PRIMARY EFFICACY PARAMETER

The primary efficacy parameter is the change from baseline to Week 8 in CDRS-R total score. The primary analysis for comparing vilazodone vs placebo will be performed using an MMRM with treatment group, pooled study center, visit, and treatment-group-by-visit interaction as the fixed effects and the baseline value and baseline-value-by-visit interaction as the covariates. An unstructured covariance matrix will be used to model the covariance of within-patient scores. The Kenward-Roger approximation (Kenward and Roger, 1997) will be used to estimate denominator degrees of freedom. This analysis will only use the observed cases of postbaseline scores without imputation of missing values.

To control the overall type I error rate for the multiple comparisons across the primary and the secondary hypotheses, a fixed sequence procedure will be applied. Details are provided in Section [10.2](#).

In addition, two sensitivity analyses, LOCF and pattern-mixture model approaches, will be performed on the primary efficacy parameter. The LOCF approach is based on an analysis-of-covariance (ANCOVA) model including treatment group and pooled study center as factors and baseline CDRS-R total score as a covariate. Another sensitivity analysis using a pattern-mixture model approach based on non-future dependent missing value restrictions (Kenward et al., 2003) will be performed to assess the robustness of the primary MMRM results to the possible violation of the missing-at-random assumption. The details of this sensitivity analysis are as follows:

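### Age group has a recruitment target but is in neither the stated randomisation strata nor the visible efficacy models; prespecifying it would give a small precision gain

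*Protocol*

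**What the plan says.** **Recruitment.** Protocol 9.3 sets two targets in one sentence. The first concerns sex: "The number of males and females will be approximately equal in both age groups". The second concerns age: "with at least 40% of the patients between 7 to 11 years of age".

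**Randomisation.** Patients are "randomized in a ratio of 2:2:1 to 1 of 3 treatment groups" (Protocol 9.1.1), and "randomization will be stratified by study center and by country" (Protocol 9.1.2). Age is not named as a stratum.

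**Primary model.** For the MMRM, SAP 10.1 names "treatment group, pooled study center, visit, and treatment-group-by-visit interaction as the fixed effects". Its only covariate is the baseline score, entered alone and interacting with visit. Protocol 9.7.5.1 lists the same terms. The LOCF and pattern-mixture sensitivity analyses use an ANCOVA with treatment, pooled centre and baseline CDRS-R. SAP 10.2 gives CGI-S a similar MMRM and an LOCF analysis.

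**Baseline checks.** Protocol 9.7.3 and SAP 8.0 summarise age by arm and test comparability. Neither says what follows if the arms differ.

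**The concern.** Age is known for every patient before randomisation, and the design treats it as important enough to set a recruitment target. Stratifying by centre cannot be relied on to balance it: 188 patients per main arm over about 60 centres is roughly three per arm per centre.

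If children and adolescents differ in CDRS-R change beyond what baseline score and centre explain, two things follow. The unexplained difference stays in the residual variance. And in the trial as realised, any imbalance in age mix moves the estimate by the residual age gap times that imbalance. The comparability test might flag such an imbalance, but an age adjustment chosen after seeing it would be post hoc and open to challenge. Deciding before unblinding avoids that.

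**Working it through.** **Inputs.** SAP 14.0: 188 per group for placebo and vilazodone, pooled SD 12.43, difference 4, power 85%, correlation 0.7, dropout 17%. SAP 10.0: two-sided 5% tests. Protocol 9.3: share of children p = 0.40, the minimum allowed. Protocol 9.7.2: Baseline to Week 8 is Visits 2-8, so six post-baseline visits. The residual age gap γ is an assumption, because the documents give none.

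**1. The plan's own sample size.** Without dropout, n = 2(1.96 + 1.036)² × 12.43² / 4² ≈ 174 per group. Under compound symmetry with correlation 0.7, six visits and dropout rising linearly to 17%, the variance of the Week 8 estimate is inflated by 1.083. Then 174 × 1.083 ≈ 188, which matches SAP 14.0. At 188 per group, power is 85.0% and SE = 12.43 × √(2 × 1.083 / 188) = 1.33. For the first interim (SD 12.3) the same method gives 184 against 182 stated. For the initial plan (SD 11.1) it gives about 151 against 160 stated, so it does not reproduce that step. Only the final figure is used below.

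**2. Chance imbalance in age mix.** SD = √(2 × 0.40 × 0.60 / 188) = 0.0505. The 95% range is ±1.96 × 0.0505 = ±9.9 percentage points, and a difference above 10 points occurs in 4.8% of trials. With p = 0.50 the range is ±10.1 points. For fluoxetine against placebo (94 and 188) it is ±1.96 × √(0.24 × (1/94 + 1/188)) = ±12.1 points.

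**3. Shift and power.** Shift = γ × imbalance. Share of variance explained: R² = 0.24γ² / 12.43². Power after full adjustment = Φ(2.996/√(1 − R²) − 1.96).

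| Assumed γ | Shift at 5-point imbalance | Shift at 10-point imbalance | R² | Power, from 85% |
|---|---|---|---|---|
| 2 | 0.1 | 0.2 | 0.6% | 85.2% |
| 4 | 0.2 | 0.4 | 2.5% | 85.9% |
| 6 | 0.3 | 0.6 | 5.6% | 86.9% |

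The 10-point shifts are 5%, 10% and 15% of the 4-point target.

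**4. Type I error.** A simulated two-arm Week 8 comparison (40,000 runs, 156 per arm) without an age term rejected in 4.9%, 5.0% and 5.0% of null trials at γ = 3, 5 and 8. With an age term the rates were 4.9%, 5.1% and 4.9%.

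**5. Form of the age term.** Suppose, as an illustration, that the age gap grows linearly over six equally spaced visits, with complete data and compound symmetry. A single age term constant over visits then estimates the average of 1/6, 2/6, …, 6/6 of the Week 8 gap, which is 0.58. About 0.42 of the gap is left unadjusted at Week 8.

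**The case against.** The strongest reply is that nothing is broken. Chance imbalance under randomisation is ordinary sampling error and is already in the SE. A reader might infer that leaving age out biases the vilazodone-placebo estimate or endangers the 5% level. The randomised allocation and step 4 show otherwise.

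A reader might also infer that age is the one factor the design fixes. The same sentence of Protocol 9.3 targets sex balance within each age group, and sex is not in the model either. A recruitment target does not show that a factor is prognostic. This stands: the case for age is that adjustment is cheap, not that the target obliges it.

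The size is modest and rests on an assumption. A 10-point imbalance is near the edge of what chance produces. At a typical 5-point imbalance the shift is 0.1 to 0.3 points against an SE of 1.33. Any part of an age effect carried by baseline CDRS-R or centre is already adjusted. This stands too.

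Finally, parts of the efficacy sections are redacted or unreadable, so an age-subgroup analysis cannot be ruled out. That prevents a claim that the plan ignores age altogether. It does not change the primary model, whose terms are fully visible.

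What survives is that adjustment costs little and can be prespecified only before unblinding. SAP 14.0 offers a yardstick: the second interim raised the main arms from 182 to 188 to hold 85% power. At an assumed γ of 5, R² is 0.24 × 25 / 154.5 = 3.9%, which lowers the need from 188.4 to 181.1 per arm.

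**Conclusion.** The point holds as a minor matter of precision and prespecification. Age group is in neither the stated strata nor the visible primary, LOCF or pattern-mixture models. The comparison remains valid without it.

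What is forgone is roughly 0.2 to 1.9 percentage points of power for residual age gaps of 2 to 6 CDRS-R points, together with a planned adjustment for a realised imbalance that could reach about 10 percentage points. These figures assume p = 0.40, an age mix not balanced by the centre strata, an SD of 12.43, and an age gap that is additional to baseline score and centre. If age is not prognostic, the gain is nil.

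**What to change.** Before unblinding, add age group (7-11, 12-17 years) and age-group-by-visit to the CDRS-R and CGI-S MMRMs in SAP 10.1 and 10.2. Add age group to the LOCF ANCOVAs and to the pattern-mixture ANCOVA. Keep all other terms. The by-visit term is needed because the target is the Week 8 contrast and a constant term may under-adjust there. It also matches the way the plan already lets baseline act by visit.

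The cost is a sentence or two in the SAP, no new data, and one degree of freedom per visit in the MMRM (six with six post-baseline visits). The loss of precision is negligible if age turns out not to be prognostic.

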#### **9.3.1 Inclusion Criteria**

To be eligible to participate in the study, patients must meet the following criteria:

1. Be able to provide informed assent and their parent/guardian/LAR and caregiver must provide written informed consent before the initiation of any study-specific procedures (Section 5.3)
2. Be a male or female outpatient, 7 to 17 years of age, inclusive, at Screening (Visit 1)
3. Meet DSM-IV-TR criteria for MDD, confirmed by K-SADS-PL, with a current depressive episode of  $\geq$  6 weeks duration at Screening (Visit 1)
4. Have a score of  $\geq$  40 on the CDRS-R at Screening (Visit 1) and Baseline (Visit 2)
5. Have a Clinical Global Impressions-Severity (CGI-S) score  $\geq$  4 at Screening (Visit 1) and Baseline (Visit 2)

6. Have a caregiver who is willing and able to be responsible for safety monitoring of the patient, provide information about the patient's condition, oversee the administration of investigational product, and accompany the patient to all study visits (Section 5.3)
7. Have normal physical examination findings, vital sign values, clinical laboratory test results, and electrocardiograms (ECG) results, or abnormal results that are determined by the Investigator not to be clinically significant
8. Must have a negative serum pregnancy test result if patient is female  $\geq$  9 years of age or has had onset of menses.

### **9.3.2                   Exclusion Criteria**

Patients who meet any of the following criteria will not be eligible to participate in the study:

#### **Criteria to be assessed at Screening (Visit 1 [unless otherwise specified])**

##### ***Psychiatric Criteria***

1. A current (within 3 months of Screening) principal DSM-IV-TR-based diagnosis of an Axis I disorder other than MDD within 6 months before Screening (Visit 1) that is the primary focus of treatment.
  - o Patients with comorbid diagnoses of learning disorders, attention deficit disorder (with or without hyperactivity), communication disorders, separation anxiety disorder, oppositional defiant disorder, and anxiety disorders will be allowed to participate in the study if these conditions are not the primary focus of treatment and all concomitant medications/limitations comply with [Appendix III](#).
  - o Patients with conduct disorder will not be allowed to participate
2. A prior diagnosis of mental retardation, or amnesia or other cognitive disorders based on DSM-IV-TR criteria
3. An imminent risk of injuring self or others or causing damage to property as judged by the Investigator
4. A suicide risk as determined by meeting any of the following criteria:
  - o Any suicide attempt within the past year
  - o A significant risk, as judged by the Investigator on the psychiatric interview or information collected in the C-SSRS

these cases):

Figure 1: Four horizontal bars representing different data series. The top bar is black with a white 'O' at the start. The second bar is black with a white 'I' at the start. The third bar is black with a white 'U' at the start. The bottom bar is black with a white 'L' at the start.

19. Pregnant, breastfeeding, and/or planning to become pregnant and/or breastfeed during the study or within 30 days following the end of study participation

20. Females who are sexually active:

Who are not practicing a reliable method of contraception that will continue for the duration of the study and within 30 days following the end of study participation. Reliable contraception is defined as:

- Surgical sterilization (eg, tubal ligation or hysterectomy)
- Oral contraceptives (consisting of an estrogen-progestin combination or progestin alone)
- Transdermally delivered contraceptives (eg, Ortho-Evra), depot injections (eg, Depo-Provera)
- Vaginal contraceptive ring (eg, NuvaRing), contraceptive implants (eg, Implanon, Norplant II/Jadelle)

Note: Females using hormonal contraceptives must have been doing so for at least 1 month before Screening (Visit 1) and must follow that product's package insert instructions concerning additional protection at times when doses might be missed.

- Intrauterine device
- Double-barrier method (ie, diaphragm plus condom)
- Exclusively sexually active with a female partner

For females who are sexually active, rhythm, withdrawal, single-barrier methods (eg, contraceptive sponge, female condom or male condom, diaphragm alone or with spermicide), emergency contraceptives (eg, Plan B as the sole plan), and abstinence are not acceptable methods of contraception during study participation.

***Criteria to be assessed at Baseline (Visit 2)***

27. A suicide risk, as determined by meeting the following criterion:

- A significant risk, as judged by the Investigator, based on the psychiatric interview or information collected in the C-SSRS

**9.3.3 Removal of Patients from Therapy or Assessment**

A premature discontinuation will occur when a patient who gave voluntary assent and/or whose parent/guardian/LAR and/or caregiver signed the ICF ceases participation in the study, regardless of circumstances, before the completion of the study visits and procedures. Patients can be prematurely discontinued from the study after careful consideration for one of the following reasons:

- Screen failure (failure to meet inclusion/exclusion criteria)
- Withdrawal of consent
- AE
- Lack of efficacy
- Protocol violation
- Noncompliance with investigational product
- Lost to follow-up
- Study terminated by Sponsor
- Site terminated by Sponsor
- Other

All randomized patients who prematurely discontinue from the study, regardless of cause, should be seen for a final assessment at an Early Termination (ET) Visit. A *final assessment* will be defined as completion of the evaluations scheduled for all patients at the end of Week 8 (Visit 8). All patients discontinuing the study prematurely should enter the 1-week, double-blind down-taper period when clinically appropriate.

Patients who discontinue from the study and do not return to the study center for final assessments must be requested in writing to return to the study center for a final assessment and return any unused investigational product. A copy of the letter, together with the source documentation, will be kept in the Investigator's files. The reason for premature discontinuation from the study will be recorded on the Study Termination Page of the eCRF. Study center staff will be contacted by the Sponsor after each premature discontinuation to ensure proper characterization of the reason for discontinuation is captured.

#### **9.3.4                   Patient Replacement Procedures**

Patients in this study who prematurely discontinue treatment will not be replaced.

[figure not shown]
### **9.4                   TREATMENTS**

Patients meeting the eligibility criteria at the end of Baseline (Visit 2) will be randomized in a double-blind fashion to 1 of 3 treatment groups: placebo, vilazodone, or fluoxetine.

#### **9.4.1                   Treatments Administered**

At Screening (Visit 1) and after consent/assent is obtained, patients will be given 3 placebo tablets and 1 placebo capsule to swallow to confirm their ability to swallow investigational product.

Investigational product in the form of tablets and capsules

Throughout the study, it is recommended that patients take the investigational product at the same time each day with food (Section 9.4.5).

Patients should participate in the double-blind down-taper period unless it is deemed not to be clinically appropriate by the Investigator.

**APPROVED**

15 Apr 2015

[REDACTED]

[REDACTED]

[REDACTED]

#### **9.4.4 Selection of Dosages in the Study**

Doses of vilazodone in pediatric patients (7-17 years of age) were selected based on modeling of available PK data from the adult healthy volunteers, as well as adult and adolescent patients (12-17 years of age) with MDD.

[REDACTED]

[REDACTED]

[REDACTED]

#### **9.4.5 Selection and Timing of Dose for Each Patient**

All investigational products should be taken orally as a single dose of 3 tablets and 1 capsule, once-daily at the same time each day, with food (see Section 9.1).

[REDACTED]

[REDACTED]

[REDACTED]

[REDACTED]

**9.4.5.1** *Screening Period*

At Screening (Visit 1) after consent/assent is obtained, placebo capsules and placebo tablets will be administered for the purposes of eligibility determination. Patients will be given 3 placebo tablets and 1 placebo capsule to swallow. If a patient is unable to swallow either the placebo capsule and/or all placebo tablets, the patient will be ineligible for study participation.

**9.4.5.2** *Double-blind Treatment Period*

Patients who meet all eligibility criteria at Screening (Visit 1) and who continue to meet all the eligibility criteria for participation in the study at the Baseline visit will be assigned a randomization number at Baseline (Visit 2) and dispensed the corresponding blister card containing tablets and capsules of double-blind investigational product for Week 1.

[REDACTED]

[REDACTED]

[REDACTED]

[REDACTED]

[REDACTED]

[REDACTED]

[figure not shown]
[figure not shown]
[REDACTED]

[figure not shown]
[REDACTED]

**9.4.5.3                   *Double-blind Down-taper Period (End of Week 8/Visit 8)***

Patients who complete 8 weeks of double-blind treatment at Week 8 (Visit 8) or patients who discontinue the study prematurely should enter the double-blind down-taper period when clinically appropriate.

